
study, the most valued aspect of the program was interaction with their peers, which informs the proposed intervention.

4. The Peer Approaches to Lupus Self-Management (PALS) Pilot Study. The PALS intervention was piloted with African American women with lupus enrolled in the SLE database at MUSC. Seven mentors were trained and paired with 21 mentees to provide modeling and reinforcement to participants by telephone for at least 60 minutes every week for 12 weeks. Mentee outcomes of self-management, disease progression (including disease activity, damage, and cytokine balance) were obtained at baseline, mid-intervention (6 weeks from baseline), and immediately postintervention (12 weeks from baseline), using validated tools. Qualitative data were also collected over the course of the study in the form of weekly mentee check-ins, mentor logs, and an end-of study focus group. While the PALS pilot lacked a control group, it provided a sense of general effect size and was used to design the current study.[107,108] At post-intervention, we observed statistically significant decreases in patient-reported disease activity (significant change score of 24,70 or 25% change in patient global assessment of overall lupus disease activity, p<0.001). incrementally improving trends in patient activation, and statistically significant decreases in depression (significant change score of 2.62 or 11% change in PHQ-8 score, p=0.05) and anxiety (significant change score of 3.52 or 15% change in GAD-8 score, p=0.018). Student t tests were also conducted to compare 2-month pre- and 2-month post-intervention hospitalization charges. Mean charges per person were \$24289 prior to intervention and \$872 post intervention, providing very strong evidence for the intervention's potential to reduce inpatient charges post intervention.[109] In addition, both mentees and mentors gave very high scores for perceived treatment credibility and service delivery, providing preliminary support for the efficacy, acceptability, and perceived credibility of the PALS intervention.[87,88,97] In summary, our preliminary studies demonstrate that in African American women with SLE, selfmanagement education delivered in weekly sessions led to improvements in lupus self-efficacy, health distress, and depression, and that more culturally targeted information and increased social support could yield more significant improvements in quality of life. More importantly, results of BLESS and IQAN studies, feedback from patients, extensive review of the literature and preliminary data from the PALS pilot study suggest that a peer mentoring intervention is credible, acceptable and likely to be effective at improving self-management, decreasing disease activity and improving quality of life in African American women with SLE. Additionally, using the same outcome measures across investigations will allow comparison of the impact of the current culturally tailored approach to the untailored "Better Choices, Better Health" intervention used in the BLESS study with this patient population.

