
Methods for AIM 3: Determine the cost and cost-effectiveness of a peer mentorship intervention on disease self-management, disease activity, and HRQOL, in African American women with SLE Resource use and cost information will be collected to inform a well-designed economic study of the cost-effectiveness of the use of peer mentors for SLE patients in the acute care setting. Cost of the intervention will include all personnel, equipment, supply and space cost associated with training and use of peer mentors, in real time dollar values. MUSC inpatient and outpatient costs of healthcare utilization of any MUSC services will be collected from MUSC administrative billing data based on ICD9/10 codes, Medicare Diagnosis Related Group (MSDRG), and CPT codes related to lupus to estimate distributions of cost for the medical care resources used. Resource use and cost data will be accessed through the Services, Pricing, and Application for Research System (SPARC Requests), which is available to MUSC-based investigators under MUSC's Clinical and Translational Science Award (CTSA). The system allows for easy access to pricing for services across the MUSC campus and its providers and focuses on billing compliance and budgetary analysis. In order to extract data from the MUSC record systems, services are

requested through an online portal and data is then provided through direct consultation. Within the SPARC system, members of the study team will also be able to track service utilization and pricing throughout the duration of the study. Questionnaire responses will be used to ascertain care resources that patients use during the study period from other hospitals or entities who are not part of the MUSC record system.

Healthcare Utilization: Stanford Patient Education Research Center Questionnaires[134,135] assessing medical outcomes such as hospital visits will be adapted to include questions related to use of other services, such as ER visits, other medical care resources of importance to patients, economic and financial barriers to use of care outside the hospital setting including loss of time at work/productivity, and any issues related to recidivism of patients once they no longer have mentor support.[136-138]

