intervention can be compared with any changes in MUSC health services utilization costs for emergency department, inpatient and outpatient care for the intervention relative to the control group. In addition to a comparison of intervention cost with average difference between MUSC costs for intervention and control group 12 months post baseline, generalized linear cost models can be estimated to examine the association of the treatment with MUSC health services costs while adjusting for patient demographics (age, gender, race/ethnicity, co-morbidities) and clinical outcomes. MUSC does not provide cost information, only charges. In addition we will estimate the impact on work loss and income by estimating the changes in days lost to illness and income based on values provided by participants. We will use the year for which the hospital charge and income data is reported and adjust for inflation as appropriate using the US Department of Labor Consumer Price Index. Inpatient and outpatient MUSC costs will be compared separately and together between the control and intervention groups. Bootstrapping methods will be used to conduct sensitivity analyses for all cost models. Sensitivity analysis will be performed by estimating a separate MUSC health services cost model while adjusting for each clinical outcome to insure robust results regarding the marginal effect of the treatment on MUSC health services costs. Park tests will be conducted to determine the best fit for the cost data in specifying the generalized linear model. In the event of many zero values, a two-part model will be used to first examine the association of the treatment with the likelihood of any MUSC costs and then the conditional generalized linear cost model, conditional on having non zero MUSC cost value for the patient. The ICR will be reported as a single ratio with no uncertainty attached to it. Therefore, standard statistical characteristics such as confidence intervals or hypothesis test to compare it to an a priori ICR from another study are not applicable. We will calculate the ICR and a clinically relevant interpretation of the outcome will be p Human Subjects Involvement and Characteristics. The Peer Approaches to Lupus Self-Management (PALS) study is a randomized controlled trial designed to examine whether a new, culturally tailored peer mentoring intervention improves disease self-management, indicators of disease activity, and health related quality of life (HRQOL) in African American women with systemic lupus ervthematosus (SLE). African American women with active SLE will be recruited as mentees and peer mentors who are considered competent in the management of their condition will be identified and recruited to provide modeling and reinforcement to participants. We will recruit mentees for 300 observations (150 mentored and 150 support group) and up to 60 mentors. Mentees and mentors will be primarily recruited from the longitudinal web-based SLE database at the Medical University of South Carolina (MUSC) in three cohorts. As part of each cohort, mentors (n=20) will be trained to deliver intervention content, prior to being paired with up to three mentees (n=50). The peer mentoring intervention will occur by twelve 60minute telephone or video sessions carried out across the course of 24 weeks. In each cohort, social support controls (n=50) will participate in a lupus support group created for this project, on the same schedule as peer mentoring sessions. All participants (mentees, mentors, and social support controls) will be assessed using validated measures of patient reported outcomes and biological indicators of disease activity at baseline, mid-intervention (3 months from baseline), immediately post-intervention (6 months from baseline), and 6 months post-intervention (12 months from baseline). For each cohort, outcomes for mentees randomized to the mentored group will be compared with the outcomes of mentees randomized to the social support control group. A booster session will be incorporated for mentored participants at 3 months post-intervention to encourage retention.

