
Inclusion criteria FOR MENTEES include: 1) African American race/ethnicity and female gender; 2) clinical diagnosis of systemic lupus erythematosus (SLE) from a physician; 3) 18 years of age or older; 4) able to provide informed consent and take part in ongoing assessment/evaluation activities (self-reported questionnaires, interviews); 5) able to commit to duration of study (12 months); and 6) able to communicate in English. Exclusion criteria FOR MENTEES include: 1) cognitive impairment; 2) active alcohol or drug abuse/dependency; 3) acute decompensation of chronic conditions precluding participation; 4) conditions that preclude participation in assessments (e.g. blindness or deafness); 5) terminal illness or life expectancy less than 18 months as evaluated by physician; and 6) current enrollment in an interventional study or trial that could affect quality of life outcomes and/or participation in one of the PI's prior behavioral trials.

Inclusion criteria FOR MENTORS include: 1) African American race/ethnicity and female gender; 2) clinical diagnosis of systemic lupus erythematosus (SLE) from a physician; 3) 18 years of age or older; 4) able to provide informed consent and take part in ongoing assessment/evaluation activities (self-reported

questionnaires, interviews, observation, activity logs); 5) able to commit to duration of study (12 months); 6) able to communicate in English; 7) disease duration > 2 years; 8) able to attend scheduled training sessions; 9) willing to provide one-on-one support to up to three African American women with SLE; and 10) PI determination of competence, maturity, emotional stability, and verbal communication skills after overall assessment during screening interview and training. Exclusion criteria FOR MENTORS include: 1) cognitive impairment; 2) active alcohol or drug abuse/dependency; 3) acute decompensation of chronic conditions precluding participation; 4) conditions that preclude participation in assessments (e.g. blindness or deafness); and 5) terminal illness or life expectancy less than 18 months as evaluated by physician. rovided similarly to other studies in the literature.[155,156]

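### The Aim 3 cost models list two covariates that cannot vary and leave out pre-randomisation charges, so the between-arm cost difference is less precise than it could be

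*Combined protocol and SAP*

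**What the plan says.** The cost models are described under Aim 3 in the Overview of Statistical Analysis Plan. Generalized linear models may be fitted to MUSC health services costs by arm, "adjusting for patient demographics (age, gender, race/ethnicity, co-morbidities) and clinical outcomes". The mentee inclusion criteria require "African American race/ethnicity and female gender", and the Study Eligibility criteria section says the same.

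The unadjusted comparison sets the cost of the intervention against the "average difference between MUSC costs for intervention and control group 12 months post baseline". Methods for AIM 3 says that inpatient and outpatient utilisation costs "will be collected from MUSC administrative billing data", with questionnaires covering care outside MUSC. Neither that section nor the list of covariates for all three aims names prior charges or prior utilisation as a covariate.

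The closest wording is a planned comparison with "any changes in MUSC health services utilization costs for emergency department, inpatient and outpatient care for the intervention relative to the control group". It defines no baseline window and is not tied to any model. In the pilot, t tests were "conducted to compare 2-month pre- and 2-month post-intervention hospitalization charges", so pre-intervention charges have been obtained before.

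The plan also provides for Park tests and for a two-part model if there are many zeros, and states: "Bootstrapping methods will be used to conduct sensitivity analyses for all cost models". The incremental cost-effectiveness ratio (ICR) is to be given without an interval or a test.

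**The concern.** Health service charges are usually skewed, with a small number of hospitalised patients carrying much of the total. The plan expects awkward data of this kind, since it provides for zeros, Park tests and bootstrapping. A woman's own earlier charges are a natural predictor of her later ones, and none of those provisions uses them. Bootstrapping describes the spread of an estimate but does not reduce it.

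Two of the four named demographic covariates explain nothing in this population, while an obtainable and plausibly prognostic one is missing. What is at stake is the width of the uncertainty around the between-arm difference in charges, and the share of that difference due to chance imbalance in prior use. Because the ICR carries no interval, a reader would not see that uncertainty if the charge difference enters the ratio.

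**Working it through.** **The plan's own figure.** No sample size, power or precision is stated for Aim 3 costs. The 123 per group in Power and Sample Size Justification is for HRQOL. It can be reached as 128.1 × 2(1 − 0.6) = 102.5, then × 1.2 = 123.0, where 128.1 per arm is the two-means size for 0.35 SD at 80% power and two-sided 0.05. It says nothing about costs.

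**1. Constant covariates.** A design matrix was built for 300 women with six columns: intercept, arm, age, gender, race/ethnicity and co-morbidities. With gender and race/ethnicity constant, its rank is 4. Both terms are absorbed by the intercept, and no estimate or standard error changes.

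**2. Inputs for the precision check.**
- From the documents: 150 mentees planned per arm, and 1:1 allocation.
- Assumed, because the documents give no SD or correlation for charges: coefficient of variation (CV) of 2 to 3, and correlation r between prior and follow-up charges of 0.3 to 0.6.

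**3. Variance reduction under linear adjustment.** The variance of the arm difference is multiplied by 1 − r².
- r = 0.3: 1 − 0.09 = 0.91, a 9% cut, equivalent to 1/0.91 = 1.10 times the sample.
- r = 0.6: 1 − 0.36 = 0.64, a 36% cut, equivalent to 1/0.64 = 1.56 times the sample.

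**4. The same on the cost scale.** With no true effect, the 95% chance range of the difference, as a share of mean charges, is ±1.96 × CV × √(2/150). Adjustment multiplies it by √(1 − r²), which is 0.954 at r = 0.3 and 0.80 at r = 0.6.

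| CV | Unadjusted | r = 0.3 | r = 0.6 |
|---|---|---|---|
| 2 | ±45% | ±43% | ±36% |
| 3 | ±68% | ±65% | ±54% |

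**5. How much baseline imbalance carries over.** If prior charges have the same CV, their chance imbalance between arms has the same unadjusted range, ±45% or ±68%. With equal spread before and after, the fraction r passes into the follow-up difference:
- CV 2: 0.3 × 45% = ±14%; 0.6 × 45% = ±27%.
- CV 3: 0.3 × 68% = ±20%; 0.6 × 68% = ±41%.

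This is the component that adjustment removes. For CV 3 and r = 0.6, 41² + 54² is close to 68², as it should be.

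**6. Simulation check.** Lognormal charges, 150 per arm, no true effect, 4,000 runs per setting, linear adjustment for prior charges. The table gives the share of trials in which the mean difference exceeded 25% of mean charges.

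| CV | Unadjusted | Adjusted | Correlation of charges |
|---|---|---|---|
| 2 | 25% | 16% | 0.52 |
| 3 | 38% | 29% | 0.45 |
| 4 | 46% | 37% | 0.39 |

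At a correlation of 0.31 with CV 2, the adjusted share was 22%, a small gain.

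**The case against.** The strongest reply is that this is a refinement to a supplementary analysis. The constant terms do no harm. The cost models are introduced as something that can be done in addition to the mean difference and the ICR. Age and co-morbidities remain as covariates, and the list for all three aims adds lupus damage, income and insurance. The wording about changes in utilisation costs could be read as a pre-post comparison. At r = 0.3 the chance range barely moves. All of this stands, except that the wording about changes gives an analyst neither a window nor a model.

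A reader might infer three stronger things that the documents do not support:

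- **That the cost difference is biased, or that imbalance in prior use passes into it in full.** Allocation is randomised, so the expected difference is unaffected, and only the fraction r carries over (step 5).
- **That a few costly women will therefore distort the ICR.** The ICR formula uses a plain cost difference. Nothing says that it includes MUSC charges or that the cost models feed it. Prior charges also cannot remove the influence of women first hospitalised during follow-up.
- **That the pilot shows how unstable these means are.** The fall from $24,289 to $872 concerns hospitalisation charges only, in two-month windows, in about 20 women, with no control group and no SD. It does not describe 12-month total charges with 150 per arm, and it does not inform the value of r.

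**Conclusion.** The point holds as one about precision and specification. Gender and race/ethnicity are fixed by eligibility and adjust for nothing. Pre-randomisation charges are absent from every Aim 3 model, although the billing source already in use could supply them. Adding them would cut the variance of the arm difference in charges by about 9% to 36%, if r is 0.3 to 0.6 and adjustment is linear. The gain is modest at the lower end, and no bias is claimed.

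The size rests on assumed values of r and CV. The 1 − r² formula was not evaluated for a log-link or two-part model, so the gain there may differ.

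The same sentence of the plan also adjusts for clinical outcomes. If follow-up values are meant, the model conditions on variables that the intervention may change. Adding prior charges while keeping that term would move the estimate from a clean randomised contrast to one that may remove part of the effect, so the two changes belong together.

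**What to change.** Specify one main model for the between-arm difference in MUSC charges, before follow-up charges are examined by arm:

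- Replace gender and race/ethnicity with MUSC charges in a fixed window before randomisation, for example 12 months, plus an indicator for any charge in that window. State the functional form in advance.
- Keep age and baseline co-morbidities.
- Leave out clinical outcomes measured after randomisation, and use them only in the sensitivity models already planned.
- Report the baseline-adjusted difference in mean charges beside the unadjusted one. Where the ICR's cost term includes MUSC charges, use the adjusted difference, and state whether it does include them.
- State whether the comparison of changes in utilisation costs is pre-post. If so, define its window.
- For women with no MUSC history, include an outside-MUSC indicator, so that no prior care is not confused with care elsewhere. Use self-reported prior utilisation only if the baseline questionnaire asks for it. Methods for AIM 3 describes questionnaire data on outside care during the study period, and the baseline content under Data Collection Schedule does not list utilisation, so this must be confirmed or added.

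The cost is a longer look-back in the billing query and a short edit to the analysis plan. The downside is incomplete prior charges for women new to MUSC or treated elsewhere, which weakens the covariate for them.

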AIM 3: Determine the cost and cost-effectiveness of a peer mentorship intervention on disease self-management, disease activity, and HRQOL, in African American women with SLE. Hypothesis 3: A peer mentorship intervention in African American women with SLE will be cost effective at improving disease self-management, disease activity, and HRQOL, as measured by quality adjusted life years (QALYS), compared with the social support control group.

An exploratory aim will be to determine the role of mediators and moderators of a peer mentorship intervention on outcomes in African American women with SLE, with the hypotheses that disease self-management will act as a mediator and depression, trust, and social support will act as moderators of the relationship between the peer mentorship intervention and disease activity and HRQOL.

The peer mentoring approach is uniquely fitted to African Americans, and this intervention has the potential to lead to health improvements for African American women with SLE that have not been attainable with other interventions. This would significantly reduce disparities and have considerable public health impact.

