
# B4. Approach

B4a. Theoretical Basis for Peer Mentoring

The Main Effect Model of Social Support posits that it is social relationships, and the support received from them, that are the primary drivers of improvements in both physical and mental health.99 The proposed peer mentoring intervention for African American women with SLE fits within a social support model that we hypothesize will influence this main effect by inducing downstream effects on health-related quality of life, mental well-being, and immune function, as it relates to disease activity. Within this model, we expect peer mentoring to reduce feelings of isolation and loneliness; provide culturally tailored, experiential, and evidence based education and information about accessing available health services; and promote behaviors that positively improve disease self-management, health-related quality of life, and disease activity.[86,100,101]

B4b. Study Overview. The Peer Approaches to Lupus Self-Management (PALS) study is a randomized controlled trial designed to examine whether a new, culturally tailored peer mentoring intervention improves disease self-management, indicators of disease activity, and health related quality of life (HRQOL) in African American women with systemic lupus erythematosus (SLE). African American women with active SLE will be recruited as mentees and peer mentors. We will recruit 300 mentees (150 mentored and 150 support group) and up to 60 mentors. As part of each wave, mentors (n=20) will be trained to deliver intervention content, prior to being paired with up to three mentees (n=50). The peer mentoring intervention will occur by twelve 60-minute telephone or video sessions carried out across the course of 24 weeks. In each wave, social support controls (n=50) will participate in a lupus support group

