created for this project, on the same schedule as peer mentoring sessions. Both conditions will be delivered via Webex, which has several advantages for this intervention: 1) Sessions are easily accessible via phone or computer, allowing participants to choose their preferred interaction style; 2) A study coordinator can host the support groups and drop in/out for monitoring purposes; 3) There are video- or voice-call options for up to 25 participants at a time; and 4) This application ensures concordant delivery methods across both arms of the study and the ability to document the frequency that voice and video options are used to adjust for participant choices in analyses. All participants (mentees, mentors, and social support controls) will be assessed using validated measures of patient reported outcomes and clinical indicators of disease activity at baseline, mid-intervention (3 months from baseline), immediately post-intervention (6 months from baseline), and 6 months post-intervention (12 months from baseline). For each wave, outcomes for mentees randomized to the mentored group will be compared with the outcomes of mentees randomized to the support group. A booster session will be incorporated for all participants (mentored and support group) at 3 months post-intervention to encourage retention.[102]

B4c. Scientific Rigor: Assuming 3 post-randomization measurement time points, level of significance p=0.05, two-tailed comparison, correlation between pairs of measurements within participants (interclass correlation) no larger than p=0.7, AR(1) covariance structure, we estimate that 123 participants per group (total n=246) are needed to detect, with 80% power, a standardized effect size of 0.35sd with 20% inflation for attrition at 12 months. This study will apply strict principles of randomized clinical trials including randomization, blinding, careful tracking of all participants and intent-to-treat analyses to ensure robust and unbiased results.

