Missing data: We will handle missing data using several techniques including multiple imputation and maximum likelihood,[149] and latent class based multiple imputation.[150] Missing data mechanisms will be examined using both univariate and multivariate methods. We will check for missing at random (MAR) by creating a missing indicator for each missing variable and study the predictors of missingness using logistic regression. If any of the fully observed covariates or outcomes become significant in the missing data model then we will use methods for MAR if we do not have any reason to believe that the missing data mechanism is not at random.

Mid-point Analyses for the protection of participants: In an effort to protect both mentors and mentees from potential deleterious effects of mentoring, a mid-point (interim) analysis will be undertaken to assess safety using 3-month post-intervention data. If mentored participants have worsened beyond a threshold, we will stop the trial for ethical concerns. For instance, if the lower confidence limits based on 95% confidence interval at the midpoint, for any one of the variables, namely depression, anxiety, and/or disease activity, is larger than 50% compared with their baseline measure, the trial will be terminated. Similarly, mentors will be monitored for depression, anxiety, and disease activity and if a worsening trajectory is observed at mid-point analyses, they will be removed from the study.

AIM 3: Determine the cost and cost-effectiveness of a peer mentorship intervention on disease self-management, disease activity, and HRQOL, in African American women with SLE.

The cost of the intervention will be compared to the outcomes of the intervention 12 months post baseline. In order to compare with previous lupus studies,[151,152] Quality adjusted life years (QALYS) will be calculated for intervention and control groups based on the SF36 outcome which will be measured 12 months post baseline. The calculation will be based on an established peer reviewed method.[153] Measuring QALYS gained relative to cost of the intervention is the preferred outcome method for the American College of Physicians (ACP).[154]

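### The Aim 3 adjusted cost models, as worded, would condition on clinical outcomes that mentoring is meant to change, so their treatment coefficient would not be the total effect on cost

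*Combined protocol and SAP*

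**What the plan says.** The AIM 3 text under Overview of Statistical Analysis Plan sets out several cost analyses.

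- An unadjusted one: a "comparison of intervention cost with average difference between MUSC costs for intervention and control group 12 months post baseline".
- In addition, and in permissive wording, generalized linear models for the association of treatment with MUSC costs, "adjusting for patient demographics (age, gender, race/ethnicity, co-morbidities) and clinical outcomes".
- A sensitivity analysis that fits a separate cost model, "adjusting for each clinical outcome to insure robust results regarding the marginal effect of the treatment on MUSC health services costs".

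None of these sentences says when the clinical outcomes used as covariates are measured. The nearest timing statement, at the start of the AIM 3 analysis text, is that "The cost of the intervention will be compared to the outcomes of the intervention 12 months post baseline".

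Two other places describe how mentoring is expected to act. Section B4a of B4. Approach expects it to work by "inducing downstream effects on health-related quality of life, mental well-being, and immune function, as it relates to disease activity". The exploratory aim in the opening Study Protocol section hypothesises that "disease self-management will act as a mediator" between the intervention and both disease activity and HRQOL.

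**The concern.** A covariate that treatment can change is not a neutral adjustment. If mentoring improves disease activity or quality of life, and better health lowers the use of care, then a model that holds those outcomes fixed compares mentored and control women as if that improvement had not occurred. Its treatment coefficient is the part of the cost effect that bypasses the adjusted outcomes. It equals the total effect only if nothing passes through them and they share no other causes with cost.

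The second condition matters separately. Clinical outcomes and costs are likely to have common causes that the model does not contain. Conditioning on a follow-up outcome then makes the arms differ on those causes, although randomisation had balanced them.

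The sensitivity analysis has the same structure. A shift in the coefficient is expected whenever the added outcome lies on the pathway, so a shift would not show fragility and stability would not show robustness. At stake is how the cost result is read: an unadjusted saving printed beside a smaller adjusted one could be taken, wrongly, as a saving explained away.

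**Working it through.** The documents state no cost effect, cost variance or power for cost, so there is no figure of the plan's to reproduce. The check is first a reading of the text, then an illustration.

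**1. Timing.** The measures are taken at baseline and at 3, 6 and 12 months (B4b), so baseline values exist. The cost-model sentence nevertheless says outcomes, lists them apart from demographics and co-morbidities, and sits in an analysis whose outcomes are placed at 12 months. The separate list of covariates for all three aims does not include disease activity or HRQOL. No sentence restricts the adjustment to baseline. Follow-up values are therefore the natural reading, though an inferred one.

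**2. Place on the pathway.** Aims 1 and 2 test whether mentoring changes self-management, HRQOL and disease activity, and B4a calls the latter two downstream effects. The further step, from these outcomes to cost, is plausible, but the documents do not quantify it.

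**3. What the adjusted coefficient estimates.** Let T be treatment and M the follow-up outcome, with within-arm SD 1.

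- Outcome: M = δT + other terms
- Log mean cost = α + τT + βM
- Total effect on log cost: θ = τ + βδ
- Mediated share: s = βδ/θ
- Coefficient of T with M in the model: τ = (1 − s)θ
- If M is measured with reliability r: (1 − rs)θ

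Assume a true total cost ratio of 0.80, so θ = ln 0.80 = −0.223. The adjusted ratio is then 0.80 raised to the power (1 − rs). The cost ratio, the shares and the reliabilities are all assumptions.

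| Mediated share s | r = 1.0 | r = 0.8 |
|---|---|---|
| 0% | 0.800 | 0.800 |
| 25% | 0.846 | 0.837 |
| 50% | 0.894 | 0.875 |
| 75% | 0.946 | 0.915 |
| 100% | 1.000 | 0.956 |

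A simulated gamma model with log link (1,000,000 participants per scenario, δ = 0.35 SD from Power and Sample Size Justification, assumed baseline-to-follow-up correlation 0.6) agreed with the table to within 0.003. In the same runs, no adjustment and adjustment for the baseline value of the outcome each gave 0.798 to 0.803, the assumed total effect.

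**4. Common cause without mediation.** Suppose an unmeasured factor raises M by 0.5 SD per unit and lowers log cost by 0.5 per unit (assumed), and nothing is mediated. Adding M shifts the treatment coefficient by 0.5 × 0.5 × 0.35 = 0.0875, a factor of exp(0.0875) = 1.091. A true ratio of 0.80 becomes 0.80 × 1.091 = 0.873 (simulated 0.870). A true ratio of 1.00 becomes 1.091 (simulated 1.091), an apparent cost increase where none exists.

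**The case against.** The strongest reply is that little depends on this model. The sentence that introduces it also plans the unadjusted average difference, and the plan compares inpatient and outpatient costs between arms, separately and together, with no outcome adjustment mentioned. The adjusted model is an addition that the text permits rather than requires. The main cost-effectiveness results are QALYs and the incremental ratio, built from group differences. All of this stands, and it bounds the point. A reader might infer that the Aim 3 cost-effectiveness ratio is biased, or that the trial would have no valid estimate of the effect on cost. The documents support neither: the ratio is not said to draw on the adjusted model, and the unadjusted comparison estimates the total effect.

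A reader might also infer that the model is bound to find no saving. That needs full mediation by outcomes measured without error. With reliability 0.8, a ratio of 0.956 remains even at full mediation.

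It can also be said that baseline values were meant. That is possible, but the text does not say so, and an analyst following it could reasonably enter follow-up values.

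Finally, the marginal treatment effect could mean the partial effect given the covariates. On that reading the coefficient is at best a direct effect, interpretable only if outcome and cost have no unmeasured common causes. It still would not answer whether mentoring changes cost.

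**Conclusion.** The point holds for the adjusted generalized linear cost model and its per-outcome sensitivity versions. On the natural reading, both condition on consequences of treatment, so their treatment coefficient omits any mediated part of the cost effect and is open to confounding that randomisation would otherwise prevent. The per-outcome models cannot serve as a robustness check on the total effect.

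The size cannot be taken from the documents, because they give no mediated share. In the error-free illustration a 50% share halves the effect on the log scale, turning an assumed saving of 20% into about 11% (1 − 0.894). Imperfect measurement softens this loss, and a common cause of outcome and cost can add bias in the absence of any mediation.

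The conclusion rests on reading the outcomes as follow-up values and on clinical outcomes influencing the use of care. It does not reach the unadjusted cost comparison, and it is not shown to reach the incremental cost-effectiveness ratio.

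**What to change.** State the time point of every covariate in the cost models. In the adjusted model, its sensitivity versions and both parts of the two-part model if used, adjust only for baseline variables: age, co-morbidities, baseline disease activity, BILD damage and HRQOL, plus pre-enrolment MUSC charges where available. Gender and race/ethnicity can be dropped, since eligibility makes them constant. Name the unadjusted or baseline-adjusted analysis as the source of the treatment effect on cost. Move any model containing post-randomisation outcomes to the exploratory mediation work and label it so. The bootstrapping and Park tests can stay as planned.

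For variables already collected at baseline, this costs only a change of wording. Prior charges are the exception. No pre-enrolment extraction window is stated, and participants recruited from outside MUSC may have no such charges. That covariate may need an extra data request, and its absence should not remove anyone from the analysis.
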